9.6 Primary Endpoint Analyses

See section 9.1.

9.7 Secondary Endpoint Analyses

See section 9.1.

9.8 Exploratory Endpoint Analyses

Not applicable

9.9 Safety Analyses

The number and percent of patients with adverse events will be reported and tabulated. Adverse events will be summarized by event type, severity, seriousness, as well as relatedness to the device and implant procedure

9.10 Interim Analyses

There will be no planned interim analyses

10 INFORMED CONSENT PROCESS

The Investigator shall obtain written informed consent from the subject using an approved Informed Consent Form (ICF) prior to any clinical investigation-related examination or activity. The rationale of the clinical investigation, as well as the risks and benefits, what participation will involve, and alternatives to participation will be explained to the subject. Ample time will be provided for the subject to enquire about details of the clinical investigation and to decide whether to participate.

All questions about the clinical investigation shall be answered to the satisfaction of the subject or the subject's legally acceptable representative. Subjects shall not be coerced or unduly influenced to participate or to continue to participate in this clinical investigation.

Each subject (or their legally authorised representative) and the person who conducted the informed consent discussion, shall sign and date the ICF. Where required, a witness shall sign and personally date the ICF. A copy of the signed ICF shall be given to the subject. The original signed ICF shall be archived in the Investigator's Site File or subject file at the investigational site.

The subject, or the subject's legally authorised representative, shall be informed in a timely manner if new information becomes available that may be relevant to the subject's willingness to continue participation in the clinical investigation. The communication of this information must be documented as an update to the ICF and re-consent of the subject.

11 ADVERSE EVENTS AND DEVICE DEFICIENCIES

11.1 Definitions

11.1.1 Adverse Event

An adverse event (AE) is any untoward medical occurrence, unintended disease or injury, or untoward clinical signs (including abnormal laboratory findings) in subjects, users or other persons whether or not related to the medical device or the procedures required for implant or use.

NOTE 1: This definition includes events related to the medical device or the comparator device.

NOTE 2: This definition includes events related to the procedures involved.

NOTE 3: For users and other persons, this definition is restricted to events related to medical devices.

11.1.2 Adverse Device Effect

An adverse device effect (ADE) is an AE related to the use of a medical device.

NOTE 1: This includes any AE resulting from insufficiencies or inadequacies in the instructions for use, the deployment, the implantation, the installation, the operation, or any malfunction of the medical device.

NOTE 2: This definition includes any event resulting from use error or from intentional misuse of the medical device.

11.1.3 Serious Adverse Event

A serious adverse event (SAE) is any AE that:

- a) led to a death,
- b) led to a serious deterioration in the health of the subject that either resulted in:
 - a life-threatening illness or injury, or
 - a permanent impairment of, or damage to, a body structure or a body function, or
 - in-patient hospitalisation or prolonged hospitalisation, or
 - medical or surgical intervention to prevent life-threatening illness or injury or permanent impairment or damage to a body structure or a body function, or
 - Chronic disease.
- c) led to foetal distress, foetal death or a congenital physical or mental abnormality, or birth defect

NOTE: Planned hospitalisation for a pre-existing condition, or a procedure required by the CIP, without serious deterioration in health, is not considered a SAE.

11.1.4 Serious Adverse Device Effect

A serious adverse device effect (SADE) is an ADE that has resulted in any of the consequences characteristic of a SAE.

11.1.5 Unanticipated Serious Adverse Device Effect

An unanticipated serious adverse device effect (USADE) is a SADE, which by its nature, incidence, severity, or outcome has not been identified in the CI500 Series Implant Hazards Analysis (Internal document 389012).

NOTE: An anticipated serious adverse device effect is an effect, which by its nature, incidence, severity, or outcome has been identified in the risk analysis report.

11.1.6 Device Deficiency

A Device Deficiency (DD) is an inadequacy of a medical device with respect to its identity, quality, durability, reliability, safety, or performance.

NOTE: Device Deficiencies include malfunctions, use errors, and inadequate labelling or information supplied by the manufacturer.

11.2 Recording and Handling of Adverse Events

Subjects shall be carefully monitored during the clinical investigation and the investigator should enquire about AEs at investigation visits.

All AEs will be recorded from the time of screening. AE recording will continue for each subject until completion of their End of Study visit. Ongoing SAEs, SADEs will be followed for 30 days, or until resolution or stabilisation of the event, whichever comes first.

Source notes should indicate the evaluation for AEs, even if none to report. All required AEs will be reported if observed, even if anticipated and/or acknowledged as a risk factor in the consent.

All AEs will have the following information documented: start and stop dates, action taken, outcome, severity and investigators opinion on the potential relationship to the AMDT and study procedures. If an AE changes in severity, the most severe (highest) grade will be captured for that event on the Adverse Events CRF.

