2 CLINICAL INVESTIGATION SYNOPSIS

Investigation title	A prospective, single-centre evaluation of Carina microphone sensitivity and maximum stable gain in adult recipients
Short title	CAMSEN
Investigation number	AI-5770
Name of Approved Medical Device on Test	Cochlear™ Carina® 2 System MET-7000
Intended use of investigational medical device(s) AMDTs for adults	The Carina Fully Implantable Middle Ear Implant System MET-7000 with the MET-7500 actuator is intended to compensate auditory deficits in individuals aged 14 or older with moderate to severe sensorineural hearing loss, and for moderate to severe conductive or mixed hearing loss when used with one of the actuator extensions. The system provides amplification via direct mechanical stimulation of the auditory system.
Name and description of comparator device/product(s)	Not applicable
Expected start date (first subject consented)	January 2020
Expected enrolment period	2 months
Expected duration per subject	1 day
Expected total duration of the clinical investigation	2 months
Number of subjects planned	Up to 20 subjects will be enrolled.
Number of investigational sites planned	Single site
Inclusion criteria	
 1. Eighteen years of age or older at the time of enrolment in the study 2. Current recipient of a Cochlear Carina System.
Exclusion criteria	
 1. Unwillingness or inability of the candidate to comply with all investigational requirements as determined by the Investigator

Objectives and Endpoints	
Objectives	Endpoints
1. To characterize Carina microphone sensitivity	Acoustic sensitivity of implanted microphone [dB FS for 0.1 Pa], in-situ, for audiometric frequencies 250-6000 Hz, median and percentiles
2. To characterize Carina microphone : accelerometer ratio for acoustic stimulation	Ratio [dB] of response of implanted microphone to response of implanted accelerometer, in-situ, for audiometric frequencies 250-6000 Hz, median and percentiles
3. To characterize Carina microphone impulse response for acoustic and actuator stimulation	Identification of the system's acoustic and vibration transfer functions including non-linear components.
4. To characterize Carina maximum stable gain.	Transfer function from Carina output to actuator [dB FS] to Carina input from implanted microphone [dB FS], for audiometric frequencies 250-6000 Hz, with and without plugged ear canal

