7 DESIGN OF THE CLINICAL INVESTIGATION

7.1 General

The investigation is a single-centre, prospective, single-arm, post-market, non-interventional, pilot clinical investigation in adults previously implanted with the Carina system.

The subjects will include men and women aged 18 years and over.

Subjects will attend one scheduled study visit to be assessed as described in the CIP Schedule of Events (section 3). At the study visit, several objective acoustic measurements will be performed that do not require active participation from the subject. No data monitoring committee will be used for this clinical investigation.

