7.2.5 Enrolment & Study Duration

The preoperative assessment will be composed of one evaluation. The ICF must be signed prior to any study related evaluation taking place.

The enrolment period for the clinical investigation is anticipated to be 1 month from the time of first subject consent to enrolment of the last subject.

The expected duration of each subject's participation in the clinical investigation, is 1 month, from the time of informed consent through to the only study visit.

The anticipated total duration of the clinical investigation is therefore 2 months.

Clinical Investigation completion is last subject visit completed. In the event of an ongoing SAEs/SADEs at the time of this last visit, the clinical investigation completion will be extended for a further 30 days, or until resolution or stabilisation of the event, whichever comes first.

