7.4 Safety Evaluations and Procedures

There will be a data safety monitor who will review all AEs, ADEs and DDs.

Safety endpoints will be a summary of AEs/ADEs and DDs from the screening to end of the last subject last visit.

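### Section 7.4 summarises safety to the last subject's last visit, section 11.2 stops recording new events at each subject's own visit, and section 9.9 does not separate events before and after the measurements

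*Combined protocol and SAP*

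**What the plan says.** - **Endpoint window.** Section 7.4: "Safety endpoints will be a summary of AEs/ADEs and DDs from the screening to end of the last subject last visit".
- **Recording window.** Section 11.2 opens it with "All AEs will be recorded from the time of screening" and closes it with "AE recording will continue for each subject until completion of their End of Study visit".
- **After the visit.** Section 11.2 adds: "Ongoing SAEs, SADEs will be followed for 30 days, or until resolution or stabilisation of the event, whichever comes first". Section 7.2.5 extends study completion on the same terms. Neither section provides for recording events that begin after the visit.
- **Visits.** Section 7.1 plans a single study visit. The schedule in section 3 places all measurements there and marks adverse events in that column only, not at screening.
- **Duration per subject.** Section 7.2.5 says it "is 1 month, from the time of informed consent through to the only study visit". The synopsis says "Expected duration per subject 1 day".
- **Analysis.** Section 9.9: "The number and percent of patients with adverse events will be reported and tabulated". It then breaks events down by type, severity, seriousness and relatedness, with relatedness taken against the device and the implant procedure. Section 11.2 collects the investigator's opinion on relatedness to the device and to study procedures, and records start and stop dates without clock times.

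**The concern.** The safety endpoint and the rule that supplies its data do not end at the same time. A new, non-serious event that an early subject reports a week after the visit falls inside the section 7.4 window and outside the section 11.2 window. Two people following the protocol could build different safety datasets from the same reports.

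The period after the measurements matters because section 8.3 names one theoretical study-specific harm: that the actuator noise could affect residual hearing. Section 3 schedules audiometry only at the same visit, so a later change would surface only if the subject reported it, and no recording of such a report is planned.

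Section 9.9 does not make up for this. Events that began before any study stimulus and events that began after it go into the same tables. The relatedness breakdown refers to an implantation that took place before the study, not to the study procedures. A percentage built this way is weak support for a statement that the measurements were well tolerated.

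**Working it through.** **1. The plan's own figures.** Section 7.2.5: 1 month of enrolment + 1 month per subject = 2 months, as stated. Synopsis: 2 months of enrolment + 1 day per subject = about 2 months, also as stated. The totals agree, but the components conflict, so both sets are carried forward. Section 8.3: 2 conditions × 3 repetitions × 10 s = 60 s of actuator noise, reproduced.

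**2. Gap between the two windows, section 7.4 read literally.** Assumptions: 20 subjects (the stated maximum), consent evenly spaced over the enrolment period E, screening at consent, visit a fixed time P after consent, and 30.4 days per month.

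- Gap for subject i, from own visit to last subject's visit: E × (20 − i)/19. The mean is E/2.
- Recorded subject-days: 20 × P.
- Endpoint subject-days: 20 × (P + E/2).

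| | Section 7.2.5 (E = 30.4, P = 30.4) | Synopsis (E = 60.8, P = 1) |
|---|---|---|
| Gap, first subject | 30.4 days | 60.8 days |
| Gap, mean | 15.2 days | 30.4 days |
| Gap, last subject | 0 | 0 |
| Recorded subject-days | 20 × 30.4 = 608 | 20 × 1 = 20 |
| Endpoint subject-days | 20 × 45.6 = 912 | 20 × 31.4 = 628 |
| Recorded share | 608/912 = 67% | 20/628 = 3% |

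**3. Share of recorded time before the measurements.** The documents do not say how long a subject stays once the measurements begin. Assume h = 0.5 to 8 hours.

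- One month: 1 − h/(30.4 × 24) = 1 − h/729.6. This is 98.9% at h = 8 and 99.9% at h = 0.5.
- One day, counted as an 8-hour visit: 1 − h/8, from 0% to 94%.
- One day, counted as 24 hours: 1 − h/24, from 67% to 98%.

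Under the synopsis duration the share is therefore not determined.

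**4. What is captured after the measurements.** This does not depend on the duration chosen.

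| Event | Planned recording |
|---|---|
| New event during the rest of the visit | Yes (11.2) |
| SAE or SADE already ongoing at the visit | Followed for up to 30 days (11.2, 7.2.5) |
| New event after the visit | None under 11.2; inside the 7.4 window if before the last subject's visit |

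**5. What start dates can separate.** Dates distinguish onset before, on and after the visit day. If recording stops at the visit, the third group is empty by construction, and every event that follows the stimulus falls on the visit day. Dates alone cannot place those events before or after the noise.

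**The case against.** The strongest reply is that the two sections do different jobs: section 7.4 gives a study-level cut-off and section 11.2 the per-subject rule. Section 7.2.5 defines completion as the last subject's visit, and section 14 closes each subject at the End of Study visit, which fits that reading. It is plausible and would remove the literal gap, but section 7.4 does not say it. It would also leave new events after the visit unrecorded.

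Other replies stand in part:

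- With one visit, that visit is the End of Study visit, so the lack of a separate column in section 3 is no defect. Asking about events at the visit can also cover the time since screening, although section 3 should say so.
- A reader might infer that section 9.9 yields only one pooled percentage. It does not: severity, seriousness and relatedness are also summarised, and the causality criteria in section 11.2.2 consider timing. What is missing is a split at the measurements and relatedness to study procedures.
- A reader might infer that nothing is recorded after the stimulus. The rest of the visit is covered, and ongoing serious events are followed.
- Safety is not among the four listed endpoints. Section 8.3 argues for low risk: 60 s, computed below 90 dB SPLeq, against a 2-hour limit at 91 dB. This limits the importance of the point but does not settle which events the safety summary contains.

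**Conclusion.** The point holds as a conflict between sections 7.4 and 11.2 and as a gap in the section 9.9 tables. It should be fixed, but it affects no sample size, hypothesis or measurement endpoint. The gap sizes (mean 15 or 30 days) rest on the literal reading of section 7.4, even spacing and 20 subjects. The limit on capturing new events to the rest of the visit rests on none of these.

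A reader might go further and conclude that the safety record lies almost wholly before exposure. The documents support that only if the one-month figure in section 7.2.5 applies and screening falls near consent; the synopsis gives one day. Exposure here must also mean the study measurements, since subjects already carry the implant throughout. Nor can one say how many subjects would be counted for background illness alone, because the documents give no background event rate.

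**What to change.** 1. Reconcile sections 3, 7.4 and 11.2, and the durations in the synopsis and section 7.2.5, to one stated window for AEs and device deficiencies.
   - If the section 7.4 window is kept, record events that subjects report to the site up to the last subject's visit. Report each subject's post-visit follow-up time, which will be unequal and zero for the last subject, so late effects in late subjects would still be missed.
   - If the section 11.2 window is kept, amend section 7.4 and limit any safety statement to events up to the end of each subject's visit.
2. In section 9.9, tabulate AEs with onset at or after the first study stimulus separately from earlier ones. Use the start dates already collected, and show visit-day events as their own category unless onset time is recorded.
3. In section 9.9, add relatedness to study procedures, which section 11.2 already collects.

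The cost is protocol wording and one table split, with no change to the stimulus, the visit or the number of subjects. Recording events that subjects report after the visit adds a little site work. An onset-time field in the eCRF and one closing call per subject (at most 20) would sharpen the data but are optional.

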8.3 Risks Associated with Participation in the Clinical Investigation

The clinical trial does not prescribe medical treatments. No interaction with medication that may be given as part of clinical routine is anticipated.

Theoretically, the stimulation of the patient's cochlea with the white noise signal used to measure maximum stable gain could damage residual hearing, if it was dangerously loud. The maximum stimulation level that can be set in the software is 85 dB MET (broadband), which is a -35 dBV drive level to the actuator (Jenkins, Pergola, & Kasic, 2007). Actuator efficiency as measured in temporal bone studies and clinically (Grossöhmichen et al., 2017) is below 120 dB SPLeq @ 1V median, so the -35 dBV corresponds to 85 dB SPLeq loudness perceived by the patient. Even at exceptionally good actuator efficiency of 125 dB SPLeq @ 1V, equivalent loudness will be below (125-35) = 90 dB SPLeq.

A stimulation level of 91 dB SPL is deemed safe for a maximum of 2 hours per day continuous exposure, it is the maximum acceptable loudness dosage for workplace noise hazards (NIOSH, 1998), below which an employer is not even required to offer hearing protection. The planned measurement duration (see below) is 2 conditions x 3 repetitions x 10s = 60s, far below the 2h limit.

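### After the single visit only serious events are followed, so a hearing-related event classed as non-serious that day may never have its final outcome or persistence recorded

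*Combined protocol and SAP*

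**What the plan says.** Section 11.2 sets the end of recording: "AE recording will continue for each subject until completion of their End of Study visit". The only follow-up beyond that point is for serious events: "Ongoing SAEs, SADEs will be followed for 30 days, or until resolution or stabilisation of the event, whichever comes first". Section 7.2.5 matches it for study completion: "In the event of an ongoing SAEs/SADEs at the time of this last visit, the clinical investigation completion will be extended for a further 30". The unit there is days, and the same alternative of resolution or stabilisation applies.

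Section 11.2 also sets what must be documented for every event, serious or not: "All AEs will have the following information documented: start and stop dates, action taken, outcome, severity and investigators opinion". The opinion meant is the one on relatedness.

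Sections 3 and 7.1 provide one study visit after screening. The audiogram, direct thresholds, microphone measurements, maximum stable gain measurement and adverse event enquiry all fall in it.

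Section 8.3 names one study-specific harm, that the white noise used for the maximum stable gain measurement "could damage residual hearing, if it was dangerously loud". It describes this harm as theoretical. Section 11.1.3 lists among several alternative criteria for a serious event "a permanent impairment of, or damage to, a body structure or a body function, or" others, including intervention to prevent such impairment.

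**The concern.** Follow-up depends on an event already being classed as serious. For a new hearing change, seriousness may depend on whether the change lasts, and only follow-up shows that. The rule is circular for the one harm the plan singles out. In a study with later visits this would hardly matter, because the next visit would show whether the symptom had gone. Here the exposure visit is also the last contact.

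Take a subject who reports dulled hearing or tinnitus after the noise, which the investigator reasonably judges non-serious that day. The event has no stop date yet, and its recorded outcome is its status on leaving. If it resolves, nobody records that. If it persists, nobody re-assesses it. With at most 20 subjects, one event classed differently moves the serious-event percentage in the section 9.9 summary by 1/20 = 5 percentage points.

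**Working it through.** **Plan's own exposure figures (section 8.3).**
- Duration: 2 conditions × 3 repetitions × 10 s = 60 s. Reproduced.
- Level at the median actuator efficiency bound: 120 − 35 = 85 dB SPLeq. Reproduced.
- Level at exceptionally good efficiency: 125 − 35 = 90 dB SPLeq. Reproduced.
- Share of the cited limit of 2 h at 91 dB SPL: 60 / 7200 = 1/120 = 0.83% by time. Scaled by energy from 91 to 90 dB, 0.83% × 10^(−0.1) = 0.66%.

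On these figures the event is unlikely. The check does not dispute them.

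**Follow-up by classification at the visit (sections 7.2.5 and 11.2).**

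| Event ongoing at the end of the visit | Recording ends | Follow-up afterwards |
|---|---|---|
| SAE or SADE | end of follow-up | up to 30 days, or resolution or stabilisation if sooner |
| Non-serious AE or ADE, hearing-related or not | the visit | 0 days |

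This treats the End of Study visit as the single visit in section 3, since the schedule shows no other.

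**Does another section fill the gap?**
- 7.2.8 marks post-investigation care as not applicable.
- 7.4 summarises safety events up to the last subject's last visit. That is a reporting window. Collection stops per subject under 11.2, and the last subject has no later time on any reading.
- 7.4, 8.4 and 11.4.2 provide for review of reported events. None schedules a contact.
- 11.4.1 allows reports to be updated as information arrives, but it concerns serious event reports.
- 14 lets withdrawn subjects stay in safety follow-up only until their scheduled End of Study visit.

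None provides follow-up for a non-serious event.

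**Rules side by side.** Section 11.2 wants a stop date and outcome for all AEs. An event ongoing at the only visit cannot have a stop date then, and no later collection is planned unless it is serious. Section 11.1.3 makes permanence one criterion for seriousness, which cannot be observed on the day of exposure.

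**Duration per subject.** The synopsis gives "Expected duration per subject 1 day"; section 7.2.5 gives 1 month from consent to the only visit. These need reconciling separately. On either figure, follow-up of a non-serious event ends at the visit.

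**The case against.** The case against giving this much weight is substantial, and most of it stands.

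- **Oversight does not depend on seriousness.** The safety monitor reviews all AEs, ADEs and device deficiencies (7.4), the sponsor's board regularly reviews all reported ADEs (8.4), and the sponsor reviews all safety data (11.4.2). A reader might infer that a non-serious hearing event escapes sponsor attention; the documents do not support that. What remains is that review works on what has been recorded, and nothing is recorded after the visit.
- **Permanence is one criterion among several.** A reader might infer that it alone decides seriousness. It does not: intervention to prevent permanent impairment also qualifies (11.1.3), and the investigator uses clinical judgement (11.2.3). A suspected lasting loss can be called serious on the day, which triggers the 30-day follow-up. The gap is confined to events judged non-serious.
- **An outcome is recorded.** Outcome is a required item for every AE, so an affected event has a status at the visit. Only the final outcome may be missing.
- **The section 9.9 summary does not report outcome.** It covers type, severity, seriousness and relatedness. A missing final outcome would not show there; the table could be affected only through the seriousness classification.
- **Detection is limited.** Bone-conduction and direct thresholds each appear once in section 3, with no stated order relative to the noise. A change would come to light mainly through the subject's report, and follow-up contact would not measure a threshold shift.
- **The event is unlikely** on the plan's own figures. That lowers the priority, and it also keeps the cost of closing the gap near zero.

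**Conclusion.** The point holds in a limited form. For an ADE or hearing-related AE that is non-serious and ongoing at the end of the single visit, the plan gives 0 days of follow-up, against up to 30 days for an SAE or SADE. Its final outcome and persistence may not be learned, although section 11.2 asks for stop date and outcome for all AEs and section 11.1.3 makes permanence one route to seriousness.

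The rule applies to all of up to 20 subjects, but it has an effect only if such an event occurs, and 60 s at a level below 90 dB SPLeq makes that unlikely. Priority is low to moderate. The endpoints in section 9.2 are unaffected.

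It would go too far to conclude that a lasting hearing change could never be identified as serious, or that the safety conclusions as a whole are unreliable. The investigator can classify the event as serious at the visit, and all reported ADEs are reviewed whatever their class.

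The conclusion assumes that the End of Study visit is the single scheduled visit and that no document outside the CIP provides for further contact.

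**What to change.** Reconcile sections 11.2, 7.2.5 and 11.1.3 by extending the plan's existing follow-up window (30 days, or resolution or stabilisation if sooner) to any ADE or hearing-related AE still ongoing at the end of the visit. Record its outcome, and re-assess seriousness under 11.2.3 when follow-up closes. Limit this to events already ongoing at the visit: recording ends there, so events that start later remain outside the plan unless that cut-off is changed too.

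This is a cheap improvement to safety-data collection. It takes about two sentences in the CIP and leaves the measurements and endpoints unchanged. The cost is one contact per affected subject, probably for few or no subjects, and possibly up to 30 days' delay in study completion if a subject seen near the end is affected.

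It would record persistence by report. Without a hearing test before and after the stimulus, it would not by itself prove a permanent threshold change, and the text should not claim that it does.
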